6.3.2.1.3 Study-Specific Daily Procedures, Days 2-6

Study Day 1 will be defined as the first 24-hour period during which Infusion #1 is given. For example, if admission occurs at 11:55 PM and the first investigational infusion occurs at 1:00 AM, then Day 1 will begin at 12:00 AM, and admission would be considered Day 0. Every subject enrolled will have a different investigational treatment schedule based on the time of tPA or mechanical thrombectomy and the subsequent first dose of 3K3A-APC or placebo. Procedures that center around the administration of investigational product may not fall on a specific study day, and therefore are outlined in section 6.3.2.2. The following procedures should be performed daily, or as indicated:

Daily

- PE (only notable changes from baseline must be recorded)
- Assessment of AEs
- Assessment of Concomitant Medications
- Vital signs, and as indicated in section 6.3.2.2 around investigational treatment
- Neurological examination: NIHSS

Laboratory Tests:

- CBC (complete blood count and platelets), Days 2-4 only; a differential must be performed if the white blood cell count is elevated.
- Chemistries (liver function, glucose and electrolytes), Days 2-4 only

• Urinalysis (dipstick or microscopic), Days 2-4 only; microscopic urinalysis must be performed if dipstick is positive for RBCs.

Once Only

 Non-contrast enhanced head CT or T1 MRI, per SOC, 24-36 hours following tPA bolus administration.

NOTE: If a CSS uses MRI as SOC at this time point, it is encouraged that the MRI protocol for this study be used. Refer to the 'Imaging Plan' for details.

6.3.2.1.4 Study-Specific Procedures, Day 7 or Discharge (+/- 3 day window)

- PE (only notable changes from baseline must be recorded)
- 1.5T MRI: T1 and T2 weighted images, as well as DWI and SWI sequences
- Assessment of AEs (through *actual* Day 7 only)
- Assessment of Concomitant Medications (through actual Day 7 only)

NOTE: Should the Day 7 visit occur on the early side of the allowed window, a phone call is required and should be documented to ensure all AEs are captured through actual Day 7 along with the required concomitant medications. Concomitant medications must also be collected through Day 30 only when a SAE occurs on or before actual Day 30.

- Assessment of Discharge Medications (medications that the subject is sent home with when discharged from the hospital)
- Vital signs (blood pressure, heart rate, temperature, respiratory rate, oxygen saturation)
- Neurological examination: NIHSS

6.3.2.1.5 Study-Specific Procedures, Day 14 (+/- 4 day window)

• Blood for serum antibody sample ('post-dose D14')

NOTE: Every effort should be made to ensure the subject is seen on Day 14 in order to collect the antibody sample. The CSS coordinator should contact the CCC to discuss alternative options available to sites for subjects who are unable to return to the CSS.

6.3.2.2 Study-Specific Procedures, Day 30 (+/- 5 day window)

- PE (only notable changes from baseline must be recorded)
- 1.5T MRI: T1 and T2 weighted images, as well as DWI and SWI sequences
- Assessment of SAEs (through *actual* Day 30 only)
- If a SAE is reported, assessment of Concomitant Medications

NOTE: Should the Day 30 visit occur on the early side of the allowed window, a phone call is required and should be documented to ensure all SAEs are captured through actual Day 30 along with the required concomitant medications.

- Vital signs (blood pressure, heart rate, temperature, respiratory rate, oxygen saturation)
- Neurological examination: NIHSS
- mRS
- Bl
- Blood for serum antibody sample ('post-dose D30')

6.3.2.3 Study-Specific Procedures, Day 90 (+/- 10 day window)

- PE (only notable changes from baseline must be recorded)
- Vital signs (blood pressure, heart rate, temperature, respiratory rate, oxygen saturation)
- Neurological examination: NIHSS
- mRS
- BI
- 1.5T MRI: T1 and T2 weighted images, as well as DWI and SWI sequences

NOTE: While MRI is preferred at Day 90, should a subject become unable to undergo MRI, a CT scan should be performed.

6.4 Special Instructions and Definitions of Evaluations

6.4.1 **Protocol Deviations and Violations**

The site monitor is responsible for collection of all protocol deviations that occur during the course of the study to ensure proper reporting in the clinical study report.

Generally, any activity that is not performed as outlined in the protocol should be categorized as a 'Protocol Deviation'. Missed visits and any procedures not performed (not attempted) for reasons other than illness, injury or progressive disability (i.e., subject is physically unable to perform test) will be reported as protocol deviations. Procedures or visits not performed due to illness, injury or disability, including procedures that were attempted but failed (i.e., blood samples unable to be drawn after multiple attempts, or weight unable to be obtained due to subject immobility) will not be reported as protocol deviations. Deviations fall into two categories, 'major' and 'minor', and are defined as follows:

Major: Any deviation that impacts safety, welfare, or rights of a study subject, or impacts the primary outcome of the study (safety assessments). Examples include: Informed Consent issues affecting a subject's rights, Inclusion/Exclusion violations, Missed Assessments affecting safety endpoints, Study Drug Administration that affects a study endpoint or the subject's welfare. A major deviation is also termed a protocol violation.

Minor: Any deviation that does not fall within the above category. Examples include: Out of Window or Missed study assessments that do not affect a study endpoint or the subject's welfare.

6.4.2 Medical History

The subject's medical history should include the standard intake history as well as all AEs occurring after signing of the informed consent form, but before the first dose of study drug.

6.4.3 Treatment History

All treatments, including administration of tPA or use of thrombectomy devices, will be recorded in the subject's medical record (source documentation) and in the eCRF. Baseline medications will be recorded 3 days prior to tPA or mechanical thrombectomy through just prior to first administration of study drug.

6.4.4 Concomitant Medications/Treatments

All medications taken following the first administration of study drug through *actual* Day 7 will be recorded. If a subject experiences a SAE between Day 7 and Day 30, then concomitant medications should also be captured through *actual* Day 30.

6.4.5 Discharge Medications

Discharge medications will be recorded in the medical record and captured in the eCRF and should include all medications that the subject is sent home with when discharged from the hospital.

6.4.6 Protocol Amendments and Study Termination

All revisions and/or amendments to this protocol must be approved in writing by the Sponsor and the CIRB. The Investigator will not make any changes to the conduct of the study or the protocol without first obtaining written approval from the Sponsor and the CIRB, except where necessary to eliminate an apparent immediate hazard to a study subject.

The Sponsor and NeuroNEXT Network reserve the right to discontinue the study at a clinical study site(s) for safety or administrative reasons at any time. Should the study be terminated and/or the clinical study site closed for any reason, all documentation and study drug pertaining to the study must be returned to the Sponsor or its representative.

6.4.7 Special Blood Sample Collection and Handling

6.4.7.1 Pharmacokinetic Sample Collection and Handling (Plasma)

PK samples will be collected from approximately 40 subjects at a sub-set of study sites to ensure adequate sampling across all dose levels. Samples should be collected following one of the doses of 3K3A-APC at the following time points: EOI and 20, 40, 60, 80 minutes after the EOI (5 total samples per subject). The Investigator can decide which dose, 2-5, will be used for PK collection. Collection of samples outside of the requested nominal time will not be a protocol deviation, but it is essential that the actual time of collection be captured for analysis.

Collection:

- Approximately 4 mL of blood will be collected into Sponsor-provided tubes containing sodium citrate and the serine protease inhibitor benzamidine.
- After blood collection, invert gently 8-10 times; samples will be held at room temperature pending centrifugation.

Processing:

- To separate plasma, blood samples will be centrifuged at room temperature within 10

 30 minutes at 3000 rpm (2000-4000 x g) for 10 minutes.
- The plasma will be removed from the blood, split into 2 equal aliquots, and stored in 2 mL labeled Cryotube[™] containers.
- Plasma will immediately be placed in a temperature-controlled (with recordings) and alarmed ≤ -70°C freezer.

Storage:

• Samples will be stored in $a \le -70^{\circ}$ C freezer at the Investigational site.

Shipping:

 Frozen samples will be batch shipped on dry ice to the central laboratory at the University of Rochester for storage. Pre-printed air bills and temperature-validated packaging will be provided by the central laboratory. Primary and back-up aliquots should always be shipped separately in order to mitigate against loss. Refer to the 'Laboratory Manual' for additional detail on the shipping frequency of samples.

Analysis:

PK analysis will occur at a second sec

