This is a multicenter, prospective, randomized, controlled, double-blinded Phase 2 study intended to evaluate the safety, PK and preliminary efficacy of 3K3A-APC following administration of tPA or mechanical thrombectomy or both in subjects with moderate to severe acute ischemic stroke. Approximately 115 subjects will be randomized, which includes the planned 88 subjects in groups of four to either 3K3A-APC or placebo (in a 3:1 ratio) and additional placebo subjects who will be enrolled during safety review pauses. This study will utilize a modified version of the continual reassessment method (CRM) in order to establish a maximum tolerated dose (MTD)¹.

For the purposes of this study, we assume an established background symptomatic intracerebral hemorrhage (SICH) rate of $3-6\%^{2-7}$. Correspondingly, the MTD will be defined as the highest dose with a DLT rate of 10% or less. Subjects will be enrolled to 3K3A-APC dose cohorts in groups of four (three to specified treatment dose and one to placebo). Subjects will generally be enrolled at the dose estimated from the assumed dose-response model and prior data to be closest to the MTD. However, the initial cohort will start at the lowest dose level (120 µg/kg) and the dose level may be escalated by no more than one dose between consecutive cohorts (there are no restrictions on dose level de-escalation). Intra-subject dose modification is not permitted during the study. After the final group of subjects is enrolled, the final MTD will be defined as the highest dose with an estimated toxicity probability less than or equal to the target toxicity level of 10%.

The design will proceed as follows:

- Enroll the first 4 subjects into cohort 1.
 - Treat one of the four subjects (chosen randomly) with placebo.
 - $_{\odot}$ Treat the other three subjects with the lowest dose: 120 µg/kg.
 - Observe the number of subjects (out of the three treated subjects) that have a DLT per study definition. Any given subject who receives only one dose of study drug and does not experience a DLT will not be included in the CRM calculation (i.e. two or more doses will need to be administered to be included).
 - Based upon the observed information from the three treated subjects, refit the assumed dose-response curve.

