3. SECONDARY ENDPOINTS

3.1 Pharmacokinetic (PK) Properties

One secondary objective of this study is to investigate the PK properties of 3K3A-APC following tPA administration in stroke subjects. PK blood samples will be collected from approximately 40 subjects at a subset of study sites to ensure adequate sampling across all dose levels. Samples should be collected following one of the doses of 3K3A-APC at the following time points: end of infusion and 20, 40, 60, and 80 minutes after the end of infusion (5 total samples per subject). The investigator can decide which dose (dose 2-5) will be used for PK collection. Collection of samples outside of the requested nominal time will not be a protocol deviation, but it is essential that the actual time of collection be captured for analysis. Samples collected for PK will only be used for PK-related analysis and method development.

PK parameters following administration of 3K3A-APC in the study will be determined using concentration data obtained via the enzyme-immunocapture assay of 3K3A-APC amidolytic activity in plasma. PK parameters will be determined by fitting a compartmental model to each subject's data. Individual subject observed and model-predicted plasma concentration over time by treatment group will be plotted on linear and semi-logarithmic axes. Descriptive statistics of PK parameters will be provided for each dose level. Additionally, the pharmacokinetic-pharmacodynamic relationship between the change from baseline in aPTT and the concurrently measured 3K3A-APC plasma concentration will be evaluated 1 hour after the end of infusion.

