Subjects who have signed consent (or whose representatives have provided surrogate consent), and meet all inclusion and exclusion criteria, can be randomized into the study. Subjects will be randomized using the NeuroNEXT Interactive Web Response System (IWRS) to either 3K3A-APC or placebo (in a 3:1 ratio). The Investigator, or designee, should randomize the subject in the IWRS to receive a unique subject number, which will also be linked to the allocated treatment assignment. Clinical staff will receive confirmation of the randomization, but remain blinded to the treatment assignment. Subjects who receive mechanical thrombectomy only should be randomized close to the start of the procedure (arterial puncture) to ensure that they continue to meet eligibility. There are 22 groups of four subjects planned, but fewer may be enrolled should the study meet either of the early stopping criteria (see section 7). If at any time enrollment is so rapid that there are two consecutive cohorts in the DLT review period, subjects will be assigned to placebo until the earlier of the two cohorts has been completely reviewed. The additional placebo subjects will be closely monitored and enrollment may be discontinued if the number enrolled exceed what was planned for the study.

The NeuroNEXT IWRS system will also serve to inform the unblinded study pharmacist at each site of the treatment assignment. Immediately after randomization, an email notification will be sent informing the unblinded site pharmacist(s) of the new subject, his/her weight, the treatment assignment, and the dose (if assigned to drug). The study pharmacist will then use this information to prepare the investigational treatment. An actual pre-dose weight for each subject is preferred, as all investigational doses will be based on this weight. If a subject's weight was estimated for the purposes of study drug dose calculation, then an actual weight must be obtained within 24 hours of Dose 1.

It is important to confirm eligibility again close to the first investigational dose as the NIHSS score may drop below 5 during the time between randomization and the first dose of study drug. For this reason, a repeat NIHSS should be assessed:

- Immediately prior to Dose 1 infusion if the subject received tPA treatment only, OR
- Immediately prior to draping the subject in preparation for mechanical thrombectomy if the subject is to receive mechanical thrombectomy alone or in combination with tPA.

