8. PRE-SPECIFIED ANALYSES OF SECONDARY OUTCOMES

8.1 Analysis of PK Parameters

An enzyme capture immunoassay method has been developed and validated by Charles River Laboratories (Reno, Nevada) for determination of 3K3A-APC activity in plasma. Brief details are included below. Tables, listings, and graphs of pharmacokinetic data will be produced by the study pharmacokineticist ([name]). These results will not be included in the FSR produced by the NeuroNEXT DCC, but will be submitted in a separate report.

PK parameters following administration of 3K3A-APC will be determined using concentration data obtained via enzyme-immunocapture assay of 3K3A-APC amidolytic activity in plasma. Based upon analysis of PK data from the Phase I study, a one-compartment IV infusion model will be used and will be parameterized in terms of the primary parameters clearance (CL) and volume of distribution (V). Secondary parameters will include C_{max} , AUC_{0-inf} , and $t_{1/2}$ and will be calculated from the primary parameters. The actual times of the beginning and end of all 5 infusions and each blood sampling time relative to the start of the first dose will be used in the modeling.

Compartmental modeling will be done using Phoenix WinNonlin Version 6.2 or higher. All analysis data and final parameter estimates for both analyses will be in SAS datasets. SAS version 9.3 or higher will be used for

data management, and to produce individual subject listing and descriptive statistics for plasma concentrations and pharmacokinetic parameters and individual subject concentration vs. time graphs. In-text graphs will be produced using SigmaPlot Version 12.5 or higher.

Observed and model-predicted plasma concentrations will be plotted on linear and semi-logarithmic axes by subject. Descriptive statistics of plasma PK parameters will be provided for each dose cohort. PK parameters will be compared among doses using descriptive statistics and graphical displays.

The analysis for the PK population will be conducted according to actual dose received. The status of the subjects will be given in a summary table by treatment group:

- Number of subjects screened
- Number of subject randomized
- Number of subjects treated
- Number of subjects who completed the study
- Number of subjects who received planned number of doses
- Number of subjects in the PK population

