For pharmacokinetic data, any concentrations that are “below lower limit of quantification (BLLQ)” will be considered 0 for the purposes of analyses.

Descriptive statistics will be reported for plasma concentrations, separately for each cohort and time point. Summary tables of pharmacokinetic tables will also be produced per treatment group for each cohort. The tables will display sample size, arithmetic mean, SD, and CV%, geometric mean and CV%, and minimum, median, and maximum. The analysis will also produce graphs showing mean +/- standard error plasma 3K3A-APC concentrations versus nominal time, per regimen and treatment group (linear and semi-logarithmic). Individual subject graphs of observed- and model-predicted plasma concentrations will also be prepared. The relationship between the change from baseline in aPTT and the concurrently measured 3K3A-APC plasma concentration 1 hour after the end of infusion will also be assessed.

Finally, a listing of individual blood sampling concentration data (PK) will be generated along with a listing of antibody development results.

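### The PK sample of about 40 subjects has no stated link to arm or dose, so coverage of every dose level is not assured, and the plan lacks a pooled PK estimate that would cope with small dose groups

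*Protocol*

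**What the plan says.** **Size and purpose.** Protocol 6.4.7.1: "PK samples will be collected from approximately 40 subjects at a sub-set of study sites to ensure adequate sampling across all dose levels". SAP 3.1 has the same sentence. No derivation, precision target or number per dose accompanies the figure of 40.

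**Who is sampled, and when.** Protocol 6.4.7.1: "Samples should be collected following one of the doses of 3K3A-APC at the following time points", and "The Investigator can decide which dose, 2-5, will be used for PK collection". Neither sentence says whether placebo subjects are among the 40.

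**Blinding.** SAP section 4: "Clinical staff will receive confirmation of the randomization, but remain blinded to the treatment assignment". Protocol 6.3.1.3 agrees. The site pharmacist is unblinded (Protocol 4.4.4), as are the statisticians who run the CRM (SAP section 7).

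**Numbers.** Protocol Synopsis, Design: "Approximately 115 subjects will be randomized, which includes the planned 88 subjects in groups of four". Each group of four has three subjects on drug and one on placebo. The rest are extra placebo subjects enrolled during safety review pauses.

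**Analysis.** SAP 8.1: "PK parameters will be compared among doses using descriptive statistics and graphical displays", and "Descriptive statistics will be reported for plasma concentrations, separately for each cohort and time point". Each subject's data are fitted with a one-compartment model. No estimate pooled over doses and no model of exposure on dose is planned.

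**The concern.** PK is a named secondary objective, and the stated purpose of sampling 40 subjects is to cover every dose level. A fixed total and a list of sites cannot do that by themselves. The CRM sets the dose of each cohort from the DLT data, and its expected allocations are very uneven. Blinded staff, with no selection rule, would also be expected to draw from placebo subjects, who have no study drug in plasma.

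The figure of 40 may therefore overstate the PK information. The only planned comparison across doses could rest on a handful of subjects at some levels, too few to show whether exposure rises in proportion to dose.

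**Working it through.** **1. Counts.** The figure of 40 has no derivation, so it cannot be reproduced. The surrounding counts can: 22 × 4 = 88 in cohorts, 22 × 3 = 66 on drug, 22 on placebo within cohorts, and 115 − 88 = 27 extra placebo subjects.

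**2. On-drug PK subjects if sampling is blind to arm.**
- All 115 eligible, with the extra placebo subjects sampled in proportion: 40 × 66/115 = 23.0.
- Cohort subjects only: 40 × 66/88 = 30.0.
- If 40 on drug is what was meant, blind sampling needs 40/0.75 = 53.3 (about 54) to 40/(66/115) = 69.7 (about 70) subjects.

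**3. Expected PK subjects per dose.** Formula: on-drug count × that dose's share of the lagged CRM allocation in Table 5 (SAP 9.1; Protocol 8.3.1). For scenario 5 the allocations 36.9/13.9/6.4/3.8 sum to 61.0, so the low-end count at 540 µg/kg is 23.0 × 3.8/61.0 = 1.4.

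| Scenario | 23 on drug (120/240/360/540) | 30 on drug | Smallest group |
|---|---|---|---|
| 1 | 4.3/3.3/3.0/12.3 | 5.7/4.4/3.9/16.0 | 3.0–3.9 |
| 2 | 4.4/3.9/4.1/10.6 | 5.8/5.0/5.3/13.9 | 3.9–5.0 |
| 3 | 5.5/5.2/4.9/7.3 | 7.2/6.8/6.4/9.6 | 4.9–6.4 |
| 4 | 7.9/6.8/4.4/3.9 | 10.3/8.8/5.8/5.1 | 3.9–5.1 |
| 5 | 13.9/5.2/2.4/1.4 | 18.1/6.8/3.1/1.9 | 1.4–1.9 |
| 6 | 17.7/3.5/1.2/0.6 | 23.1/4.6/1.6/0.8 | 0.6–0.8 |

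These are expectations, so a given trial could fall below them. Even if all 40 were on drug, the smallest expected group would be 5.2/6.7/8.5/6.8/2.5/1.0 in scenarios 1 to 6.

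**4. Precision of a geometric mean.** Between-subject CV is not in the documents; 30% to 40% is assumed. On the log scale σ = √ln(1 + CV²), which is 0.294 at 30% and 0.385 at 40%. The 95% interval multiplies and divides the estimate by exp(t(0.975, n−1) × σ/√n).

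| n | CV 30% | CV 40% |
|---|---|---|
| 3 | 0.48–2.07 | 0.38–2.60 |
| 5 | 0.69–1.44 | 0.62–1.61 |
| 23 (pooled) | 0.88–1.14 | 0.85–1.18 |

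For n = 3 at 30%: 4.303 × 0.294/√3 = 0.729, and exp(0.729) = 2.07.

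**5. Precision of a dose slope.** Regress log exposure on log dose in 23 subjects. The 95% half-width is t(0.975, 21) × σ/√S, where S is the sum of squared deviations of ln dose from its mean. At 30% CV:
- Scenario 1: S = 7.75, so 2.080 × 0.294/√7.75 = 0.22.
- Scenario 5: S = 5.58, so 2.080 × 0.294/√5.58 = 0.26.
- Scenarios 2 to 4 lie between these. Scenario 6, with almost everyone at the lowest dose, gives 0.32.
- At 40% CV the range over scenarios 1 to 5 is 0.29 to 0.34.

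Over the 540/120 = 4.5-fold dose range, a half-width of 0.22 to 0.26 is a factor of 4.5^0.22 = 1.39 to 4.5^0.26 = 1.48 in relative exposure.

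**The case against.** **Blind sampling is an inference.** No section says that PK subjects are drawn without regard to arm. The wording refers to doses of 3K3A-APC, and the IWRS and the pharmacist know the assignment, so 40 drug-treated subjects is a possible reading. This stands, and is why 23 to 30 is conditional. The wording does not settle it, because Protocol 3.1 and the vital-signs note in 6.1 use the drug name for infusions that placebo subjects also receive. The lower figure also assumes that all 27 extra placebo subjects are enrolled and sampled in proportion; Protocol 4.4.4 allows their enrolment to be stopped.

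**The smallest groups come from the CRM.** In scenarios 5 and 6 it treats only 3.8 and 1.3 subjects at 540 µg/kg on average, and no PK rule can exceed those numbers. This stands. A reader might infer that groups of one to three are the general expectation. Below 3, they arise only in scenarios 5 and 6; scenario 1 reaches 3.0 at 360 µg/kg at the low end only.

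**Cohort probably means dose cohort.** A reader might take the by-cohort summary of concentrations to mean the 22 CRM cohorts, with about one PK subject each and no definable SD. Elsewhere SAP 8.1 speaks of each dose cohort and of actual dose received, and SAP 3.1 of each dose level. The word is loose, but that reading is not supported.

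**The objective is descriptive.** No proportionality test or precision target is promised, and Phase 1 already reported clearance and volume independent of dose (Protocol 2.5). This limits the weight of the point. It also supports pooling, and the individual fits already supply every input.

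**Conclusion.** The claim to cover all dose levels is not assured, because no stated mechanism links PK sampling to arm or dose. That holds however the 40 is counted.

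The size is conditional. If sampling is blind to arm, about 23 to 30 of the 40 are on drug. The smallest expected dose group is then about 3 to 4 in scenario 1, 4 to 6 in scenarios 2 to 4, and under 2 in scenarios 5 and 6, the last mostly a consequence of the CRM. Descriptive comparison among such groups is imprecise, whereas the same subjects pooled give a usable estimate; those figures rest on an assumed CV of 30% to 40%. PK sampling also needs at least two infusions, so early discharge could lower the counts; no rate is given.

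A reader might go further and say that adequate sampling is not delivered, or that the PK objective cannot be met. The documents do not support either: *adequate* is undefined, the objective is descriptive, and 23 on-drug subjects are informative when pooled.

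**What to change.** **SAP 8.1.** Keep the per-dose summaries. Add, as the main PK estimate, clearance and volume pooled over all drug-treated PK subjects with 95% intervals. Add a power model of log AUC and log Cmax on log dose, reporting the slope with its 95% interval; the slope also checks the dose-independence on which pooling rests. Where concentrations are summarised by cohort and time point, replace cohort with dose level.

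**Protocol 6.4.7.1 and SAP 3.1.** State the target as drug-treated subjects with evaluable PK, or restate it as 40 sampled with about 23 to 30 expected on drug. Replace *ensure* unless the unblinded statisticians track evaluable PK counts by dose. Tracking cannot raise a dose group above what the CRM treats there, so it complements the pooled analysis and does not replace it.

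**Cost.** The pooled analysis uses data already collected and needs only SAP wording. Tracking can use the existing unblinded statisticians and the IWRS, leaving site blinding intact. If the target becomes 40 on drug under blind sampling, about 14 to 30 more subjects would have to be sampled (54 − 40 to 70 − 40), with no additional enrolment.
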